2.2 Endpoints

Primary performance endpoints

- Sensitivity: Proportion of spontaneous hypoglycaemic episodes detected by the hyposafe H02 compared to the total number of validated¹ spontaneous hypoglycaemic episodes after 12 weeks of monitoring (from visit 5 to visit 10)
- Positive predictive value: Proportion of validated¹ spontaneous hypoglycaemic episodes detected by the hyposafe H02 compared to the total number of alerts from the hyposafe H02 after 12 weeks of monitoring (from visit 5 to visit 10)

Secondary performance endpoints

- Overall sensitivity: Overall proportion of hypoglycaemic episodes detected by the hyposafe H02 compared to the total number of validated² hypoglycaemic episodes after 12 weeks of monitoring (from visit 5 to visit 10)
- Overall positive predictive value: Overall proportion of validated² hypoglycaemic episodes detected by the hyposafe H02 compared to the total number of alerts from the hyposafe H02 after 12 weeks of monitoring (from visit 5 to visit 10)
- Sensitivity: Proportion of insulin-induced hypoglycaemic episodes detected by the hyposafe H02 compared to the total number of insulin-induced hypoglycaemic episodes

¹ Validated by self-measured blood glucose (SMBG) or clinical hypoglycaemia according to subject's experience

² Validated by self-measured blood glucose (SMBG), plasma glucose (PG) or clinical hypoglycaemia according to subject's experience

- Positive predictive value: Proportion of insulin-induced hypoglycaemic episodes detected by the hyposafe H02 compared to the total number of alerts from the hyposafe H02
- Number of participants with a satisfactory EEG Quality test
- Change in impedance (from visit 5 to visit 10)
- Number of device complaints (from visit 4 to visit 10)
- Mean glucose level at the time of a hypoglycaemia alarm

Primary safety endpoint

- Number of AEs 17 weeks after implantation (from visit 3 to visit 12)

Secondary safety endpoint

- Number of adverse device effects (ADEs) 17 weeks after implantation (from visit 3 to visit 12)

Secondary usability endpoints

- Development in discomfort over time (visit 5 to visit 10)
- User satisfaction (visit 8)
- Mean number of hours of use per hyposafe H02 device (from visit 4 to visit 10)
- Response to hypoglycaemia alarm (from visit 5 to visit 10)
- Assessment of alarm fatigue (visit 12)

3 Study design - overview

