The hypoglycaemic alarms will be classified according to categorisation displayed in Table 2 (true and false, positive and negative hypoglycaemia alarms), and presented as described for primary performance endpoint.

Table 2 Categorisation of hypoglycaemic episodes

Episodes categorised as			
PG > 3.9mmol/l	+ alarm	+/- clinical hypoglycaemia ^{a)}	False positive 
	- alarm	+/- clinical hypoglycaemia ^{a)}	True negative 
PG 2.0 – 3.9mmol/l	+ alarm	+/- clinical hypoglycaemia ^{a)}	True positive 
	- alarm	+ clinical hypoglycaemia ^{a)}	False negative 
		- clinical hypoglycaemia ^{a)}	True negative 
PG < 2.0mmol/l	+ alarm	+/- clinical hypoglycaemia ^{a)}	True positive 
	- alarm	+/- clinical hypoglycaemia ^{a)}	False negative 
PG not measured	+ alarm	+ clinical hypoglycaemia ^{a)}	True positive 
		- clinical hypoglycaemia ^{a)}	Not categorised 
	- alarm	+ clinical hypoglycaemia ^{a)}	Not categorised  False negative ^{b)} 

^{a)} According to subject (No strict definition is given)

^{b)} If hypoglycaemic episode was severe (i.e. requiring assistance from third person whether being help for carbohydrate ingestion, glucagon injection or contact to health care person), the episodes should be characterised as false negative

PG; plasma glucose

Data from **EEG quality test** at the visit 4 and visit 10 will be compared graphically.

The **impedance** is expected to be below 5 kOhm at all times. No trend in the measurements for each subject should be apparent over time, except perhaps a small decline in the beginning. Any change in impedance over time (from visit 5 to visit 10) will be summarised descriptively and presented by subject.

The **number of device complaints** will be tabulated and presented by device part.

Mean blood, plasma or interstitial **glucose level at the time of an alarm** will be summarised for insulin-induced hypoglycaemia and spontaneous hypoglycaemic episodes, separately.

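### In two cells of Table 2 the alarm itself decides whether an episode counts, so primary sensitivity is 100% by construction there; Table 2 and section 2.2 also define different reference episodes

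*Combined protocol and SAP*

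**What the plan says.** Section 2.2 defines primary sensitivity as detected spontaneous episodes over all validated spontaneous episodes. Its first footnote gives the validation rule: "Validated by self-measured blood glucose (SMBG) or clinical hypoglycaemia according to subject"'s experience. The rule does not mention the alarm and sets no glucose threshold.

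Section 7.5.1 then has the sponsor classify with Table 2. The rows that matter are:

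- Middle glucose band with an alarm: "PG 2.0 – 3.9mmol/l + alarm +/- clinical hypoglycaemia ^{a)} True positive". Symptoms are irrelevant.
- Same band, no alarm, no symptoms: "clinical hypoglycaemia ^{a)} True negative".
- No glucose reading, alarm, symptoms: "PG not measured + alarm + clinical hypoglycaemia ^{a)} True positive".
- No glucose reading, no alarm, symptoms: "alarm + clinical hypoglycaemia ^{a)} Not categorised". Footnote b makes an exception for severe episodes: "the episodes should be characterised as false negative".
- High glucose with an alarm, whatever the symptoms: "PG > 3.9mmol/l + alarm +/- clinical hypoglycaemia ^{a)} False positive".

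The same table serves the secondary performance endpoints: "The hypoglycaemic alarms will be classified according to categorisation displayed in Table 2".

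**The concern.** Sensitivity has its usual meaning only if an episode is a reference episode, or is not one, before the device result is known. In two cells of Table 2 the device result settles that question. Detections enter both numerator and denominator, while logged misses on the same evidence enter neither.

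Sensitivity is a primary endpoint. Section 7.1 says the results may guide optimisation of the algorithm, and section 8.10 says the report will be used in further development and approval of the device. Because section 2.2 and Table 2 do not describe the same reference episodes, the sponsor could also obtain different primary values from the same log books.

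**Working it through.** The documents give no expected sensitivity, predictive value or episode count, so there is no figure to reproduce. Sensitivity is taken as TP/(TP+FN) from Table 2. The plan does not write this formula out, but it gives no other rule for uncategorised episodes.

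**1. Cell by cell**

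| Evidence | Alarm | No alarm | Reference episode under 2.2? |
|---|---|---|---|
| PG > 3.9, no symptoms | FP | TN | No |
| PG > 3.9, symptoms | FP | TN | Yes, read literally |
| **PG 2.0–3.9, no symptoms** | **TP** | **TN** | Yes, if SMBG validation means PG ≤ 3.9 (assumption) |
| PG 2.0–3.9, symptoms | TP | FN | Yes |
| PG < 2.0, with or without symptoms | TP | FN | Yes (same assumption if symptom-free) |
| **No PG, non-severe symptoms** | **TP** | **Uncategorised** | Yes |
| No PG, severe | TP | FN | Yes |

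Only the two bold cells allow a TP but no FN. The full glucose bands are not affected: symptomatic misses at 2.0–3.9, all misses below 2.0 and severe unmeasured misses stay false negatives.

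**2. Direction.** Let a, b be TP and FN outside the two cells, and d, u the detections and logged misses inside them.

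- Table 2: (a+d)/(a+b+d).
- Both cells included in both alarm states: (a+d)/(a+b+d+u). This is no higher, because u adds to the denominator only.
- Both cells excluded in both alarm states: a/(a+b). Table 2 minus this is bd/[(a+b)(a+b+d)], which is at least 0.

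As a check, all counts 0–5 were enumerated in six cells (a, b, and detections and misses in each of the two cells, with a+b > 0) against the four symmetric rules (each cell in or out). That is (6⁶ − 6⁴) × 4 = 181,440 comparisons. The symmetric rule was never above Table 2; it was equal in 13,615.

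**3. Size under assumed counts**

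| Assumed a, b, d, u | Table 2 | Inclusion | Exclusion |
|---|---|---|---|
| 5, 5, 5, 5 | 10/15 = 67% | 10/20 = 50% | 5/10 = 50% |
| 9, 9, 1, 1 | 10/19 = 53% | 10/20 = 50% | 9/18 = 50% |
| 7, 3, 2, 8 | 9/12 = 75% | 9/20 = 45% | 7/10 = 70% |

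If the detection probability q is the same everywhere and a share f of episodes lies in the two cells, Table 2 gives q/[q+(1−f)(1−q)]. For q = 0.50 this is 0.556, 0.625, 0.714 and 0.833 at f = 0.2, 0.4, 0.6 and 0.8.

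If both cells count as reference episodes, and only then, reported sensitivity is S/(1−m), where S is the sensitivity with both cells included and m is the share of logged reference episodes that are misses in the two cells. S = 50% becomes 0.50/0.95 = 53% at m = 5% and 0.50/0.90 = 56% at m = 10%.

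**4. Against section 2.2.** The unmeasured, non-severe, symptomatic miss is an explicit conflict: 2.2 validates it on symptoms alone and Table 2 drops it. The 2.0–3.9 conflict is an inference, because 2.2 gives no threshold. The symptomatic PG > 3.9 conflict holds if 2.2 is read literally, and it can work the other way. Assume 10 symptomatic episodes at 2.0–3.9 (5 alarmed) and 10 at PG > 3.9 (9 alarmed). Literal 2.2 then gives (5+9)/20 = 70%, and Table 2 gives 5/10 = 50%. The net direction against literal 2.2 is therefore not fixed.

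**The case against.** **The middle band has a physiological rationale.** Section 1.1.2 places clear EEG changes at about 2.0 mmol/L, so a silent device above that need not be called a failure. This supports leaving symptom-free cases out of sensitivity. It does not support crediting alarms in the same cell as hits.

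**Section 2.2 may govern the denominator.** If it does, unmeasured symptomatic misses count whatever their Table 2 label. But section 7.5.1 names Table 2 as the classification, and the two texts then give different answers. That is part of the problem.

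**The PG > 3.9 conflict is weak.** Symptoms in 2.2 could be read as standing in only when no glucose value exists. That reading is possible, but the plan does not state it.

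**Logging may be unequal.** Section 7.5.3 expects subjects to measure glucose after an alarm, so silent symptom-free lows will be recorded less often. If such misses are logged at 20% of the assumed rate, inclusion in the first illustration gives 10/16 = 62.5% against 66.7%; at 0% there is no difference. This stands: inclusion may correct little, and part of the bias lies in the data. Exclusion still gives 50% in that illustration.

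**Requiring symptoms is not fully independent of the alarm**, because action prompted by an alarm may avert them. This also stands, and it favours counting the band regardless of symptoms.

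**Induced episodes are less exposed.** They have frequent plasma glucose measurement, so the unmeasured cell should rarely arise there.

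**The study is a small descriptive one.** No comparative analysis is planned, and about 12 subjects are judged sufficient. That limits the consequence but does not remove it, since the estimate is itself the result.

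**Conclusion.** The concern holds. Table 2 has exactly two cells in which detections count and logged misses cannot, and relative to any symmetric handling of those cells it leaves primary sensitivity unchanged or raises it. That direction needs no assumption about case mix; it rests only on computing sensitivity from Table 2 as TP/(TP+FN).

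The size cannot be derived from the documents. The equal-detection illustrations put it between 3 points (few symptom-free episodes) and 17 points (half of them symptom-free). Section 4.2 enrols subjects who are unaware of hypoglycaemia, have a recent severe episode, or both, so symptom-free low readings are plausible.

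The disagreement with section 2.2 is explicit for unmeasured symptomatic episodes and a matter of reading in the other two places. This should be fixed before classification. Type I error and power are not affected.

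**What to change.** 1. Define a reference episode from glucose and symptoms only, apply it identically in the alarm and no-alarm rows of Table 2, and reword section 2.2 to match, including its glucose threshold.
2. For 2.0–3.9 mmol/l, choose one symmetric rule as primary and report the other as supportive. Either count the band regardless of symptoms, so that a silent case becomes a false negative, or require symptoms in both alarm states. The first is the more independent of the alarm.
3. Score unmeasured symptomatic episodes as true positive with an alarm and false negative without. Because Table 2 gives clinical hypoglycaemia no strict definition, add a supportive analysis limited to episodes with a measured glucose, and tabulate the episodes now left uncategorised.
4. State how symptomatic episodes with PG > 3.9 count. Giving the glucose value precedence would be a change to section 2.2 and should be written as one.
5. State the remaining limitation: symptom-free misses that are never measured or logged stay invisible under any rule, and alarms prompt measurement.

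The cost is rewording plus a few tables. Section 7.5.1 already requires glucose and symptom data for classification. Its list of log-book items does not name symptom status, so the sponsor should confirm that it is captured.

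Correcting the two cells leaves reported sensitivity lower or unchanged. Requiring symptoms at 2.0–3.9 can also move the positive predictive value. In the first illustration with 5 further alarms at PG > 3.9 (assumed), it is 10/15 = 67% under Table 2 or inclusion, and 5/15 = 33% if alarmed symptom-free cases become false positives. If they are set aside it is 5/10 = 50%, but that departs from the all-alerts denominator in section 2.2 and would have to be stated there.

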4.1 Definition of the overall subject population

Between 12 and 20 subjects with type 1 diabetes and impaired awareness of hypoglycaemia will be enrolled in the study to ensure a number of subjects completing the study of at least 12.

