4.2 Inclusion criteria

For a subject to be eligible, all inclusion criteria must be answered “yes”:

1. Informed consent obtained before any study related activities³
2. Type 1 diabetes diagnosed at least five years prior to inclusion in the study
3. Age 18-70 years
4. Impaired awareness, i.e. defined as unaware by the Pedersen-Bjergaard scale (section 6.1.5) *and/or* history of at least one severe hypoglycaemia⁴ within the preceding year

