6.1.5 Hypoglycaemia awareness status

The Pedersen-Bjergaard method (24) and recent history of severe hypoglycaemia will be used to assess hypoglycaemia awareness status at visit 1.

For the Pedersen-Bjergaard method, the subject will be asked: "Do you recognise symptoms when you have a hypo?" and can select one of the following answers:

- Always
- Usually
- Occasionally
- Never

Subjects answering "occasionally" or "never" (i.e. unaware according to Pedersen-Bjergaard method) *and/or* who has experienced at least one severe hypoglycaemic episode within the preceding year will be classified as having impaired awareness of hypoglycaemia.

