7.5.3 Usability endpoints

All usability endpoints will be analysed using the FAS.

Development in discomfort over time

Data from questionnaires regarding discomfort related to the implanted device will be tabulated and presented by week and discomfort category and compared over time (visit 5 to visit 10).

Assessment of alarm fatigue

Data from questionnaire regarding alarm fatigue at visit 12 will be tabulated and presented by category of sensitivity and false alarm(s).

User satisfaction

Subject user satisfaction at visit 8 will be summarised based on the specific questionnaire.

Usage of external device

The mean number of hours the hyposafe H02 day or night device has been connected to the implant from visit 4 to visit 10 will be summarised. Summaries will be presented for daytime and night-time, separately.

Response to hypoglycaemia alarm

The number of preventive actions, i.e. the number of hypoglycaemia alarms where subject was able to take preventive action as instructed (acknowledge the alarm by key press, measure blood glucose, and in case of low blood glucose; ingest a carbohydrate rich meal) compared to the total number of hypoglycaemia alarms from visit 5 to visit 10 will be tabulated.

8 Ethics

The study will be conducted according to the Declaration of Helsinki (23) and approved by the local ethical committee before commencement. The use of the hyposafe H02 must be approved by the Danish Health and Medicines Agency before initiation. Only information relevant for the study will be collected. As UNEEG™ medical is a private data responsible the current private health research project will not been notified to the Danish Data Protection Agency. Data will be handled in accordance with the Act on Processing of Personal Data.

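### An alarm with no glucose reading is classified by an undefined self-report and can never be a false positive; this biases sensitivity upward and shifts PPV in a direction that depends on the denominator

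*Combined protocol and SAP*

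**What the plan says.** Section 2.2 defines the two primary performance endpoints on validated spontaneous episodes. Its first footnote accepts either a glucose reading or the subject's own experience: "Validated by self-measured blood glucose (SMBG) or clinical hypoglycaemia according to" that experience. The PPV divides by all alerts: "compared to the total number of alerts from the hyposafe H02 after 12 weeks of monitoring (from visit 5 to visit 10)".

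Section 7.5.1 has the sponsor classify alarms through Table 2. With an alarm and a known glucose value, symptoms play no part: above 3.9 mmol/l is a false positive and 3.9 or below is a true positive, with or without symptoms. In the row headed "PG not measured", symptoms decide:

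- alarm with symptoms: true positive;
- alarm without symptoms: not categorised;
- no alarm with symptoms: not categorised, or false negative if the episode was severe.

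Footnote a describes clinical hypoglycaemia as "According to subject (No strict definition is given)".

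On the population, section 4.1 says "Between 12 and 20 subjects with type 1 diabetes and impaired awareness of hypoglycaemia will be enrolled in the study". Section 6.1.5 asks "Do you recognise symptoms when you have a hypo" and classes those answering occasionally or never as unaware. A severe episode in the preceding year also qualifies.

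Section 7.5.3 shows that the alarm is live. The instructed response is to "acknowledge the alarm by key press, measure blood glucose, and in case of low blood glucose", eat. The log book holds both alarms and glucose readings (7.5.1).

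**The concern.** The reference used to judge an alarm should be sound and independent of it. In this row it is neither. The report has no criteria, comes from people selected for impaired awareness, and is made knowing that the device has signalled. Table 2 itself sets symptoms aside when an alarm has a glucose value, so the weaker standard applies only where nothing can check it. The possible outcomes are also one-sided: such an alarm may help the device or drop out, but cannot count as a false positive.

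The row is asymmetric for sensitivity too. The same unmeasured, non-severe symptomatic episode is a success if the device alarmed and uncategorised if it did not.

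The study is meant to verify that the device works before a larger study (1.2), and its report is to support further development and approval (8.10). With at least 12 completers planned and few spontaneous episodes expected (7.5.1), a handful of such entries could move either primary figure.

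**Working it through.** The plan gives no expected PPV, sensitivity or precision (7.1), so there is no figure to reproduce. The scoring rules below come from Table 2 and section 2.2. All rates are assumptions.

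**PPV.** Let p be the true PPV, u the share of alarms without glucose, s1 the symptom-report rate after a true unmeasured alarm, and s0 the rate after a false one. Assume measured alarms are correctly classified and checking is unrelated to true status.

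- True positives per alarm: TP = (1−u)p + u[p·s1 + (1−p)·s0].
- PPV over all alerts (2.2 wording) = TP. Its shift from p is u[(1−p)·s0 − p(1−s1)]. This is positive when false alarms reported as felt outnumber true alarms not felt, and negative in the reverse case.
- PPV with uncategorised alarms dropped = TP / {(1−u) + u[p·s1 + (1−p)·s0]}. Every unmeasured alarm that remains adds equally to numerator and denominator, so the figure can only rise.
- Bounds with all unmeasured alarms false, or all true: (1−u)p to (1−u)p + u.

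**Sensitivity.** Take 100 non-severe symptomatic episodes with true sensitivity S and a share m measured, all measured values being at or below 3.9. Table 2 counts all 100·S alarmed episodes as true positives, measured or not, but only 100·(1−S)·m of the others as false negatives. Sensitivity = S / [S + (1−S)m].

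With 100 alarms, p = 0.5, s1 = 0.6, s0 = 0.3 and, separately, S = 0.5:

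| Share measured | PPV, all alerts | PPV, uncategorised dropped | PPV bounds | False alarms scored true | Sensitivity from Table 2 |
|---|---|---|---|---|---|
| 90% | 49.5/100 = 49.5% | 49.5/94.5 = 52.4% | 45–55% | 1.5 | 50/95 = 52.6% |
| 75% | 48.75/100 = 48.75% | 48.75/86.25 = 56.5% | 37.5–62.5% | 3.75 | 50/87.5 = 57.1% |
| 60% | 48/100 = 48.0% | 48/78 = 61.5% | 30–70% | 6 | 50/80 = 62.5% |

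The sign of the all-alerts shift depends on the inputs. At p = 0.5 and u = 30%:

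- Strong prompting by the alarm (s1 = 0.7, s0 = 0.5): 0.3 × (0.25 − 0.15) = +0.03, so PPV is 0.53 over all alerts and 0.60 with uncategorised alarms dropped.
- Weak recognition without prompting (s1 = 0.3, s0 = 0): 0.3 × (0 − 0.35) = −0.105, so PPV is about 0.40 over all alerts and 0.53 with uncategorised alarms dropped.

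Over a grid of p from 0.3 to 0.7, u from 10% to 50%, and five s1/s0 pairs (s1 from 0.3 to 0.9, s0 from 0 to 0.5), the shift runs from −0.25 to +0.16 over all alerts. With uncategorised alarms dropped it runs from +0.01 to +0.27.

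**Safeguards.** The missing-data rule (7.4) covers withdrawn subjects only. No glucose-confirmed analysis is planned. CGM is worn for two periods of about 5 days, roughly 10 of 84 days (12%), and Table 2 does not name it as a reference.

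**The case against.** A reader might infer that the rule inflates the primary PPV. The documents do not establish that. Section 2.2 divides by all alerts, and on the tabulated inputs that puts PPV slightly below the true value. Impaired awareness by itself predicts unfelt true episodes, which lowers an all-alerts PPV. It does not predict symptoms at normal glucose. Inflation needs either prompting by the alarm, at an unknown rate, or the removal of uncategorised alarms, which no section states. Table 2 nevertheless leaves their place in the denominator open.

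It is also too strong to say that the report cannot confirm hypoglycaemia, or that subjects were enrolled mainly for not recognising symptoms. The entry criterion begins "Impaired awareness, i.e. defined as unaware by the Pedersen-Bjergaard scale (section 6.1.5)" but is joined by and/or to a recent severe episode, and no split is given. The order of log-book entries is not stated. What stands is that the report is undefined and not blind to the alarm.

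Symptom validation is prespecified in 2.2, so this is a design weakness and not a contradiction. Subjects are told to measure glucose at each alarm, so the row should be a residual, of unknown size.

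On sensitivity, footnote 1 of 2.2 read alone would count an unmeasured symptomatic episode as validated with or without an alarm, which restores 50/100 in the illustration. But 7.5.1 classifies through Table 2, which leaves the episode without an alarm uncategorised.

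Finally, a glucose-confirmed rule can do harm if its denominator is left unstated. Over all alerts it would give 45%, 37.5% and 30% at 90%, 75% and 60% checked, against a true 50%. It also leaves symptoms deciding the 2.0–3.9 mmol/l row when there is no alarm. Both points stand, and the first shapes the fix.

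**Conclusion.** The point holds as a weakness in the reference standard that should be repaired before analysis. An alarm without glucose is decided by a weak, non-independent report, with true positive or uncategorised as the only outcomes. For PPV, no single direction can be claimed: either way over all alerts, upward if uncategorised alarms are dropped. For sensitivity, Table 2 as written biases upward whenever some non-severe symptomatic episodes without an alarm go unmeasured, even if every report is correct. The size is 7.1 points in the illustration with true sensitivity 50% and 75% measured, and 2.6 to 12.5 points for 90% to 60% measured. These sizes rest on assumed rates and would be small if nearly all episodes were measured.

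**What to change.** In 7.5.1 and Table 2:

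1. Give unmeasured alarms with reported symptoms their own category. Report its count and the count of all alarms without a glucose reading.
2. Prespecify glucose-confirmed PPV, with glucose-checked alarms as the stated denominator. Prespecify glucose-confirmed sensitivity, excluding unmeasured non-severe episodes whether or not there was an alarm. Count severe episodes needing third-party help in the same way with or without an alarm.
3. Report these beside the current symptom-inclusive figures. State whether uncategorised alarms are in the PPV denominator, align footnote 1 of 2.2 with Table 2, and give bounds with all unmeasured alarms taken as false and as true.
4. State that glucose-confirmed PPV is unbiased only if checking is unrelated to true status. The parallel condition for sensitivity is that measuring is unrelated to whether the alarm sounded. For example, with S = 0.5 and 90% of alarmed but 60% of other episodes measured, it gives 45/(45 + 30) = 60%.

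The cost is plan wording, extra table rows and no new data collection. Fewer alarms are classified: on the tabulated inputs, 75 instead of 86.25 (13% fewer) at 75% checked, and 60 instead of 78 (23% fewer) at 60%. Precision falls accordingly, and the figures may be less favourable.

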7.5 Endpoint analysis

7.5.1 Performance endpoints

All performance endpoints will be analysed using the FAS as well as the PP analysis set.

Primary performance endpoint

The primary performance endpoints are defined as the sensitivity and positive predictive value of the hyposafe H02 based on spontaneous hypoglycaemic episodes.

Spontaneous hypoglycaemic episodes are recorded by subjects in the log book throughout the study. This includes information on blood glucose measurements before treating the episode, alarms given by the hyposafe H02 device and information on whether the subjects was able to treat him/herself or was asleep when the episode occurred.

A hypoglycaemic episode will be characterised as treatment emergent if the onset of the episode is on or after the first day the hyposafe H02 device switched to “*alarm on*”-mode and no later than the last day of the wearing the external device. Data on treatment emergent hypoglycaemic episodes are presented in terms of the number of subjects with at least one episode (N) and the number of episodes (E).

Hypoglycaemic episodes will be defined as nocturnal (i.e. during night-time) if they occur during sleep (as reported by the subject) and/or are registered by the hyposafe H02 night device.

Data from blood glucose measurement and clinical hypoglycaemia (according to subject’s experience) will be used by UNEEG™ medical to classify a hypoglycaemic alarm according to categorisation displayed in Table 2 (true and false, positive and negative hypoglycaemia alarms). As blood glucose values are lower than plasma values, a constant factor of 1.11 is used to convert concentration in whole blood to the equivalent concentration in plasma (25).

Sensitivity and positive predictive value will be calculated for daytime and night-time, separately.

Secondary performance endpoints

Insulin-induced hypoglycaemia is performed twice for each subject, with frequent assessments of plasma glucose levels. As the number of spontaneous hypoglycaemic episodes reported during the study may be relatively small, data from the insulin-induced hypoglycaemia will be added to calculate the overall **sensitivity and positive predictive value** of the hyposafe H02 (spontaneous and insulin-induced hypoglycaemia episodes) after 12 weeks of monitoring (from visit 5 to visit 10).

The sensitivity and positive predictive value will also be calculated based data from the insulin-induced hypoglycaemic episodes only.

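### Table 2 lets third-party rescue decide the category in one cell only, so a subset of un-alarmed severe episodes can escape the primary sensitivity calculation

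*Combined protocol and SAP*

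**What the plan says.** Section 2.2 defines primary sensitivity as detected spontaneous episodes over validated spontaneous episodes. Its footnote 1 gives two routes to validation: "Validated by self-measured blood glucose (SMBG) or clinical hypoglycaemia according to" the subject's experience. Footnote 2, for the overall endpoints, adds plasma glucose. Third-party assistance is not a route in either footnote.

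Section 7.5.1 has the sponsor classify episodes with Table 2, using glucose and clinical hypoglycaemia. Footnote a of the table describes the clinical item as "According to subject (No strict definition is given"). Severity enters only through footnote b: "If hypoglycaemic episode was severe (i.e. requiring assistance from third person" and so on, "the episodes should be characterised as false negative". Footnote b is attached only to the cell with no glucose value, no alarm and clinical hypoglycaemia present.

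The same section says that the log book holds the glucose value from before treatment and "information on whether the subjects was able to treat him/herself or was asleep when the episode occurred".

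Under section 4.2, subjects qualify by being unaware on the awareness scale and/or by a "history of at least one severe hypoglycaemia" in the preceding year.

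**The concern.** Footnote b shows that the sponsor accepts rescue by another person as evidence of a missed episode even without a glucose value. Yet the rule operates only if the subject also reports clinical hypoglycaemia. In a population chosen largely for impaired awareness, and with about half of hypoglycaemic episodes occurring during sleep (section 1.1.2), a rescued subject may be poorly placed to make that report.

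At stake is the count of false negatives in a primary endpoint. In the 2.0–3.9 band without reported symptoms, a rescued episode enters the calculation as a success if the device alarmed and leaves it as a true negative if the device did not. Inclusion then depends on the result being measured. The overall sensitivity, which uses the same table, has the same problem.

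**Working it through.** The plan gives no sensitivity target, expected episode count or severe-event rate, so there is no figure to reproduce. The check is to route an un-alarmed, third-party-assisted episode through every combination of glucose band and subject report.

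| Glucose (mmol/l) | Subject reports clinical hypoglycaemia | Table 2 category, no alarm, severe |
|---|---|---|
| below 2.0 | yes | false negative |
| below 2.0 | no | false negative |
| 2.0–3.9 | yes | false negative |
| 2.0–3.9 | no | **true negative** |
| above 3.9 | yes | true negative |
| above 3.9 | no | true negative |
| none | yes | false negative (footnote b) |
| none | no | **no row** |

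Of the 8 combinations, 4 are false negatives, 3 are true negatives and 1 has no row. The two above 3.9 are not at issue if the value was taken before treatment, since such an episode may not be hypoglycaemia. Two remain, in bold.

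**Glucose 2.0–3.9, nothing reported.** In the rows headed "PG 2.0 – 3.9mmol/l", an alarm gives a true positive whatever the subject reports; no alarm and no report gives a true negative. Under footnote 1 of section 2.2, a self-measured value in this range validates the episode and puts it in the denominator (taking 3.9 from Table 2 as the limit, since footnote 1 states none). The two sections therefore give different sensitivities for the same data.

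**No glucose value, nothing reported.** In the rows headed "PG not measured", the no-alarm branch has only the line with clinical hypoglycaemia. Footnote 1 does not validate this episode either, so it is left out under both sections.

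**Size, with assumed counts.** Sensitivity = TP/(TP + FN). If *m* un-alarmed severe episodes were left out, including them gives TP/(TP + FN + *m*). Starting from 80.0% in each row:

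| Assumed TP, FN | *m* = 0 | *m* = 1 | *m* = 4 |
|---|---|---|---|
| 32, 8 | 32/40 = 80.0% | 32/41 = 78.0% | 32/44 = 72.7% |
| 16, 4 | 16/20 = 80.0% | 16/21 = 76.2% | 16/24 = 66.7% |
| 8, 2 | 8/10 = 80.0% | 8/11 = 72.7% | 8/14 = 57.1% |

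For scale, 12 completers over 12 weeks give 12 × 12/52 = 2.77 person-years. One such episode is 1/2.77 = 0.36 per person-year and four are 4/2.77 = 1.44, in these two cells alone. Four should be read as an upper illustration. The smaller denominators are relevant because section 7.5.1 expects that spontaneous episodes may be few and calculates day and night separately.

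**The case against.** - **Most severe misses are already counted.** A reader might infer that primary sensitivity omits severe failures as a class. It does not. Below 2.0 mmol/l every un-alarmed episode is a false negative, and so is one at 2.0–3.9 with reported symptoms. Section 1.1.2 places clear EEG changes at about 2.0 mmol/l, so the deepest episodes are captured. This stands and limits the point to a subset.
- **The subject's report is loosely defined.** A subject who learns of the rescue and logs it may be recorded as having clinical hypoglycaemia, which makes both cells false negatives. This also stands: misrouting is possible, not certain. But nothing in the plan says that rescue implies a positive report, so the outcome depends on unwritten judgement by the sponsor.
- **Post-rescue glucose values.** A reader might infer that a value above 3.9 taken after carbohydrate or glucagon turns a miss into a true negative. Section 7.5.1 specifies the pre-treatment value, which largely closes this route. Table 2 does not repeat the condition, so a clarifying phrase is enough.
- **The conflict between section 2.2 and Table 2 is wider than severe episodes.** True; it affects every un-alarmed 2.0–3.9 episode without reported symptoms. That supports reconciling the two sections and does not remove the severe cases.
- **Rescues could appear as adverse events.** They could, since adverse events are asked about at each contact. They would still be absent from sensitivity.
- **No decision rests on the figure.** The study is small and uncontrolled, with no target. That moderates the consequence, but sensitivity remains a primary endpoint.

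**Conclusion.** The point holds in limited form. Because third-party assistance decides the category in one cell only, un-alarmed severe episodes in two combinations can leave the Table 2 calculation: one as a true negative, in conflict with section 2.2, and one for want of a row. Leaving out misses can only raise sensitivity. With one to four such episodes and the assumed starting counts, the drop on inclusion runs from 2.0 percentage points (one added to 40) to 22.9 (four added to 10). With none there is no change. These figures rest wholly on assumed counts; the documents support the direction but not a magnitude.

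A reader might also infer that an alarmed rescue with neither a glucose value nor reported symptoms should become a true positive. The documents do not support that: the alarm itself may have prompted someone to help, so the assistance is not independent evidence of hypoglycaemia.

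**What to change.** Before any episode is classified:

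1. Apply footnote b to every un-alarmed severe episode with pre-treatment plasma glucose of 3.9 mmol/l or below, or with no pre-treatment value, whatever symptoms the subject reports.
2. Add the missing row (no glucose value, no alarm, no clinical hypoglycaemia), with severe scored as false negative.
3. Add third-party assistance as a validating criterion in footnotes 1 and 2 of section 2.2 for these un-alarmed episodes, and reconcile that section with Table 2.
4. State in Table 2 that glucose means the pre-treatment value named in section 7.5.1.
5. List all severe episodes by alarm yes/no. Leave alarmed severe episodes with neither glucose nor reported symptoms as not categorised, and show them in this listing.

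With items 1 and 2, 6 of the 8 combinations are false negatives; the other 2 are those with pre-treatment glucose above 3.9.

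The cost is wording only: severity is already defined in the protocol and the log book already records ability to self-treat. Reported sensitivity may be slightly lower. When glucose is unmeasured and nothing is reported, a miss would count while an alarmed episode would not. That is conservative, and the listing makes it visible.
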